#### **12.6.3.4 CYP2A6 Activity**

CYP2A6 activity will be measured in plasma on Day 0, Day 6 and Day 91. In this study the CYP2A6 activity will be calculated using the metabolic ratio of trans 3' hydroxycotinine and cotinine, as described in Section 7.1.4 “CYP2A6”. Descriptive statistics of the values and changes on Day 6 and Day 91 from Day 0 and supportive listings will be provided.

The analysis will compare the log-transformed Day 6 values between the THS 2.2 Menthol and mCC arms and between the THS 2.2 Menthol and SA arms. ANCOVA models will be used with terms for log-transformed baseline, sex, average daily mCC consumption over the last 4 weeks as reported during screening and randomization arm. No adjustment will be made for multiple comparisons. If the results from the Day 6 analysis are significant (one-sided p-value < 0.025) then the statistical significance will be repeated for the analysis at the Day 91 values. The SAS code to be used is similar to the model reported in Section 12.6.1.3 "Sensitivity Analysis".

Geometric LS means for each product along with the ratio (THS 2.2 Menthol : mCC) and 95% CI will be presented in the tables

CYP2A6 activity will also be examined to compare the reductions in THS 2.2 Menthol vs. SA using the same methodology as above.

If there are any CYP2A6 assessments performed within 5 half-lives since the use of a concomitant medication affecting CYP2A6 activity, the analysis will be repeated by excluding these assessments for both the PP Set and FAS

All summaries and analyses will be performed on the FAS and PP Set.

The data will be presented in the below outputs:

TFL number	Title
TABLES	
15.2.4.62.1	Descriptive Statistics of CYP2A6 Activity (%) – PP Set
15.2.4.62.1.1	Descriptive Statistics of CYP2A6 Activity (%) Excluding Assessments

TFL number	Title
	within 5 Half-Lives of a Concomitant Medication Affecting CYP2A6 Activity - PP Set
15.2.4.62.2	Descriptive Statistics of CYP2A6 Activity (%) – FAS
15.2.4.62.2.1	Descriptive Statistics of CYP2A6 Activity (%) Excluding Assessments within 5 Half-Lives of a Concomitant Medication Affecting CYP2A6 Activity - FAS
15.2.4.63.1	Analysis of CYP2A6 Activity (%) – PP Set
15.2.4.63.1.1	Analysis of CYP2A6 Activity (%) Excluding Assessments within 5 Half-Lives of a Concomitant Medication Affecting CYP2A6 Activity – PP Set
15.2.4.63.2	Analysis of CYP2A6 Activity (%) – FAS
15.2.4.63.2.1	Analysis of CYP2A6 Activity (%) Excluding Assessments within 5 Half-Lives of a Concomitant Medication Affecting CYP2A6 Activity – FAS
LISTINGS	
15.3.6.20	Listing of CYP2A6 Activity and Changes from Baseline

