- Oxysterol will be measured in the study to verify that the reduction observed in animal models of disease upon smoking cessation and switching to candidate MRTP (in house data) is also observed in humans.
- CYP2A6 activity, the enzyme involved in nicotine metabolism will be assessed in this study to evaluate if the use of THS 2.2 Menthol impacts the activity of this enzyme.
- Lung function including Diffusion capacity for lung CO (DLCO), Forced expiratory volume in 1 second (FEV1), force vital capacity (FVC), vital capacity (VC), total lung capacity (TLC), forced residual volume (FRV), inspiratory capacity (IC), maximum expiratory flow (25-75) will be assessed in this study as it has been shown that some of these parameters may be improved early on after smoking cessation and are markers correlating with early but still reversible changes occurring in distal airway upon smoking (Verbank et al, 2006; Sansores et al., 2001).

Other parameters such as human smoking topography, product evaluation, and subjective effects related to smoking including smoking urges and withdrawal symptoms will be evaluated.

Twenty four-urine will be collected in this study as it is a well-established method to measure the levels of excretion of BoExp. Four-hour urine fraction will also be collected to better understand its accordance with 24-hour urine in the perspective of using such fraction in future ambulatory studies thereby minimizing operational and subject constraints.

As part of the characterization of the study population it is important to measure variables that have been shown to be related to nicotine dependence and product reinforcing value. Based on prior tobacco research these factors include age, gender, ethnicity, educational and socio-economic status, tobacco use history, expectations of the effects of the products tested, nicotine exposure, health and mental health status and use of psychoactive substances. In order to capture, these data, subjects will be asked questions about their socio-economic status at screening. Such data would allow comparing populations across studies.

All subjects will be asked to provide their own mCC according to their anticipated needs for the whole confinement period in order to minimize any changes in their smoking behavior.

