12.1.5 Significance Level for Inferential Analysis

Unless stated otherwise, all statistical tests will be two-sided and conducted at the 5% level, and all quoted confidence intervals will be two-sided 95% confidence intervals.

The primary endpoints will be tested using a multiple testing procedure to preserve the overall alpha level by simultaneously testing the endpoints using a closed procedure with each test performed at an one-sided alpha level of 2.5%. This implies that statistical significance is required for all primary endpoints in order to be able to make confirmatory claims about any of the endpoints.

Further details will be provided in the SAP.

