12.7.2 Descriptive Analysis

In general, exploratory endpoints will be summarized as described in Section 12.1.3 on the FAS.

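### SAP 12.6.3.4 tests CYP2A6 activity one-sided without naming a side and makes Day 91 significance depend on the result, although the protocol's question has no direction

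*SAP*

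**What the plan says.** Protocol 4.2 gives the reason for measuring CYP2A6: it "will be assessed in this study to evaluate if the use of THS 2.2 Menthol impacts the activity of this enzyme". The endpoint is exploratory (Protocol 3.4.3; SAP 5.3). Protocol 12.7.2 plans description for this class of endpoint: "In general, exploratory endpoints will be summarized as described in Section 12.1.3 on the FAS". For tests, Protocol 12.1.5 sets the default: "Unless stated otherwise, all statistical tests will be two-sided and conducted at the 5% level".

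SAP 12.6.3.4 adds a model-based comparison on the log scale, THS against mCC and THS against SA, by ANCOVA and without multiplicity adjustment. The Day 6 condition reads "If the results from the Day 6 analysis are significant (one-sided p-value < 0.025". What follows when that condition is met is given for the later visit: "then the statistical significance will be repeated for the analysis at the Day 91 values". On reporting, it says "Geometric LS means for each product along with the ratio (THS 2.2 Menthol : mCC) and 95% CI will be presented in the tables". The only directional word in the section is in the sentence on abstinence: "CYP2A6 activity will also be examined to compare the reductions in THS 2.2 Menthol vs. SA". The section also promises descriptive statistics at Day 6 and Day 91, with no condition attached.

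**The concern.** A one-sided p-value is undefined until its side is named. The same Day 6 estimate could give p = 0.01 on one side and p = 0.99 on the other, so two programmers working from SAP 12.6.3.4 could disagree on whether Day 91 significance is evaluated at all.

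Naming a side would remove that ambiguity but would still not fit the question, which is whether activity changes. CYP1A2 makes a useful contrast. SAP 12.6.2.4 applies the same one-sided rule to it, but there Protocol 4.2 expects a decrease and Protocol 12.2 gives an effect size. Nothing comparable exists for CYP2A6.

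At stake is the formal reading of an enzyme that, by Protocol 7.5.2.3, governs the conversion of nicotine to cotinine. A real change in the untested direction would be labelled non-significant at Day 6 and would carry no significance statement at Day 91.

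**Working it through.** **Threshold.** One-sided 0.025 and two-sided 0.05 both cut at z = 1.960 (t = 1.980 on 118 df). The SAP rule is therefore one tail of the protocol's default test, and moving to two-sided 5% leaves the critical value in the tested direction unchanged.

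**Check of the set-up.** The plan states no power for CYP2A6, so there is no CYP2A6 figure to reproduce. The general set-up (log scale, SD = √ln(1 + CV²), one-sided 2.5% t-tests, 80:40 at Day 5 and 40:40 for Total NNAL) was checked against the 50% column of the power table (Protocol Table 23; SAP Table 20). The product of the five powers is 93.9% against 94% stated, and 97.9% against 98% stated. The columns for larger reductions agree less closely and are not used here.

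**Inputs.** The sample size is 80 THS and 40 mCC (Protocol 6.3, 12.2); THS against SA is also 80:40. The documents give no CV or effect for CYP2A6, so both are assumptions: CV 0.3, 0.5 and 0.7, and a true ratio of 1.2 in the untested direction. On the log scale 1/1.2 = 0.833 gives the same results by symmetry.

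**Formulas.** SE = SD × √(1/80 + 1/40) = SD × 0.1936. Non-centrality δ = ln(1.2)/SE, with ln(1.2) = 0.1823. Probabilities come from the non-central t on 118 df.

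| Assumed CV | Log SD | δ | Significant, two-sided 5% | Significant, one-sided 2.5% on the other side |
|---|---|---|---|---|
| 0.3 | 0.294 | 3.207 | 89% | <0.0001% |
| 0.5 | 0.472 | 1.993 | 51% | 0.004% |
| 0.7 | 0.631 | 1.491 | 32% | 0.03% |

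With CV 0.5 and a ratio of 1.3, δ = 2.868 and the figures are 81% and <0.0001%.

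**Without a CV.** In standardized log-scale differences from 0.2 to 0.8 (115 df), two-sided significance runs from 17.6% to 98.4%. The wrong-side chance is at most 0.14%.

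**What the plan would still show.** The two-sided 95% CI for the Day 6 ratio excludes 1 exactly when the two-sided 5% test rejects. In the CV 0.5, ratio 1.2 case it therefore excludes 1 about 51% of the time, even though the one-sided label would almost never read significant.

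**The case against.** The strongest reply is that little is hidden. The section tabulates the THS:mCC ratio with a 95% CI, which is two-sided by the protocol default and by the code it points to in SAP 12.6.1.3 (alpha = 0.05 with confidence limits). It also gives unconditional descriptive statistics at both days, in the FAS and the PP Set. A shift either way would appear there. This stands: a reader might infer that a change in the untested direction goes unseen, and the documents do not support that.

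Three other stronger readings also fail.

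- **That the tested side is lower, so a rise cannot be declared.** The word *reductions* belongs to the sentence on THS against SA. The SAP's hypothesis of a lower level (5.5.1) concerns biomarkers of exposure, which CYP2A6 is not. The referenced code names no tail. For THS against mCC the side is simply unspecified.
- **That the SAP breaches the protocol.** The two-sided default allows stated exceptions, and the SAP states one. Protocol 12.7.2 speaks only in general terms, so an added exploratory model is no breach either.
- **That Day 91 is not analysed unless Day 6 is significant.** The rule conditions statistical significance, not the estimate. For the parallel Day 5/Day 90 rule, the SAP revision history describes only the p-value as conditional. The wording leaves the Day 91 ratio and CI unclear rather than withheld.

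It can also be said that no nicotine or cotinine analysis depends on the CYP2A6 significance call. That is correct, and the bearing on the nicotine results is interpretive only.

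What the reply does not answer is that the rule as written cannot be applied without choosing a side, and that any choice leaves one half of a two-directional question without a test.

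**Conclusion.** The point holds as a mismatch between test and question on an exploratory endpoint. Whichever side is adopted, a change in the other direction cannot be declared significant at Day 6 and does not open the Day 91 significance evaluation. At 80:40, with an assumed CV of 0.5 and a true ratio of 1.2 in that direction, the chance is below 0.01% against about 51% two-sided. Across CVs of 0.3 to 0.7 it is at most 0.03%, against 89% to 32%. These figures rest on an assumed CV and an assumed ratio, and they measure the loss of a significance label, not of detection.

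The study's success criterion and its confirmatory comparisons are untouched. This is a minor point, worth correcting because the rule is ambiguous as written and the correction is nearly free.

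**What to change.** In SAP 12.6.3.4, replace the one-sided rule and its Day 91 condition with the following: report the THS:mCC and THS:SA ratios with two-sided 95% CIs and two-sided nominal 5% p-values at Day 6 and at Day 91, both whatever the Day 6 result, and label them exploratory.

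This fits the protocol's question and its default for tests, and it settles whether the Day 91 ratio and CI are always shown. The cost is a one-sentence change to the SAP and the same model run at both days. No new data are needed, and no power is lost in whichever direction would have been tested.

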#### **12.6.3.5 Ames Mutagenicity Test**

The 24 hour urine collection for the Ames mutagenicity test will be on Day 0, Day 5 and Day 90.

Descriptive statistics of the values and percent changes on Day 5 and Day 90 from baseline of the YG1024+S9 mutagenicity will be provided, along with listings.

All summaries will be performed on the FAS, and PP Set.

The data will be presented in the below outputs:

TFL number	Title
TABLES	
15.2.4.64.1	Descriptive Statistics of Ames Mutagenicity Test (YG1024+S9) (units) – PP Set
15.2.4.64.2	Descriptive Statistics of Ames Mutagenicity Test (YG1024+S9) (units) – FAS
LISTINGS	
15.3.5.1	Listing of Ames Mutagenicity Results and Changes from Baseline

#### **12.6.3.6 Visual Inspection of the Tobacco Plugs**

The collection of the tobacco plugs from the THS 2.2 Menthol products will be performed on Days 1 to 5, and Days 30, 60 and 90. The number and percentage of tobacco plugs showing each of the following criteria will be summarized by day: “No overheating”, “White spot(s) inside the tobacco plug”, “Ashes inside the tobacco plug and burnt paper” and “Missing”.

All summaries will be performed on the FAS only.

The data will be presented in the below outputs:

TFL number	Title
TABLES	
15.2.4.65	Descriptive Statistics of Visual Inspection of the THS 2.2 Menthol Tobacco Plugs Data – FAS
LISTINGS	
15.3.6.21	Listing of Visual Inspection of the Tobacco Plugs

#### **12.6.3.7 Oxysterols**

Plasma concentrations of  $6\alpha$ -hydroxy- $5\alpha$ -cholestane,  $7\alpha$ -hydroxycholesterol,  $5\alpha,6\alpha$ -epoxycholestanol, 7-ketocholesterol,  $7\beta$ -hydroxycholesterol,  $5\beta,6\beta$ -epoxycholestanol, 24(R)-hydroxycholesterol, 25-hydroxycholesterol, 27-hydroxycholesterol, TC, 22(R)-hydroxycholesterol and  $4\beta$ -hydroxycholesterol will be measured in plasma on Day 0, Day 6 and Day 90 Visit (2nd Day).

Descriptive statistics of the values and changes on Day 6 and Day 91 from Day 0 and supportive listings will be provided.

All summaries and figures will be performed on the FAS and PP Set.

The data will be presented in the below outputs:

TFL number	Title
FIGURES	
15.1.2.11.1	Oxysterol Parameters Arithmetic Mean and 95% CI – PP Set
15.1.2.11.2	Oxysterol Parameters Arithmetic Mean and 95% CI – FAS
TABLES	
15.2.4.66.1	Descriptive Statistics of Oxysterol Parameters – PP Set
15.2.4.66.2	Descriptive Statistics of Oxysterol Parameters – FAS
LISTINGS	
15.3.6.22	Listing of Oxysterol Data and Changes from Baseline

#### **12.6.3.8 Product preference analysis**

The product preference as asked at admission will serve as a sensitivity analysis for the product exposure.

All summaries will be produced for the Safety populations.

These data will also be presented categorized separately by product preference and by product use categorization (see Section 6.3.3.1 “Dual-use”).

The data will be presented in the below outputs:

TFL number	Title
TABLES	
15.2.4.67	Descriptive Statistics of Average Daily Product Use in Ambulatory Period by Preferred Product Declared at Admission – FAS
15.2.4.68	Descriptive Statistics of Product Use Categories by Preferred Product Declared at Admission – FAS
LISTINGS	
15.3.1.5	Listing of Product Preference Results

#### 12.6.3.9 Concordance Between 24-hour Urine Collection and 4-hour Urine Fraction

The concordance will be investigated between MHBMA, 3-HPMA, S-PMA, total NNAL, total 1-OHP, total NNN, 4-ABP, 1-NA, 2-NA, o-tol, CEMA, HEMA, B[a]P, HMPMA, S-BMA, NEQ, 8-epi-PGF2 $\alpha$  and 11-DTX-B2 (expressed as concentration adjusted for creatinine in 24-hour urine collection and concentration adjusted for creatinine in 4- hour urine fraction) at baseline and at Day 90 Visit.

Scatterplots between each pair of variables will be produced showing the Spearman Rank correlation coefficient on the plot. In adition Bland-Altman (Altman and Bland 1983) plots of the data will be produced including the mean of the differences and the 95% CI. These will be produced for the FAS and presented in an Appendix of the CSR.

In these scatterplots the data from the 24-hour urine collection will be on the x-axis.

The data will be presented in the below outputs:

TFL number	Title
FIGURES	
15.1.2.12.1	ScatterPlot of Urinary MHBMA Concentration Adjusted for Creatinine from 24 hour Urine Collection versus 4 hour Urine Fraction at Baseline and Day 90 Visit – FAS
15.1.2.12.2	Bland-Altman Plot for Concordance of Urinary MHBMA Concentration Adjusted for Creatinine from 24 hour Urine Collection and 4 hour Urine Fraction at Baseline and Day 90 Visit – FAS
15.1.2.13.1	ScatterPlot of Urinary 3-HPMA Concentration Adjusted for Creatinine from 24 hour Urine Collection versus 4 hour Urine Fraction at Baseline and Day 90 Visit – FAS
15.1.2.13.2	Bland-Altman Plot for Concordance of Urinary 3-HPMA Concentration Adjusted for Creatinine from 24 hour Urine Collection and 4 hour Urine Fraction at Baseline and Day 90 Visit – FAS
15.1.2.14.1	ScatterPlot of Urinary S-PMA Concentration Adjusted for Creatinine from 24 hour Urine Collection versus 4 hour Urine Fraction at Baseline and Day 90 Visit – FAS

TFL number	Title
15.1.2.14.2	Bland-Altman Plot for Concordance of Urinary S-PMA Concentration Adjusted for Creatinine from 24 hour Urine Collection and 4 hour Urine Fraction at Baseline and Day 90 Visit – FAS
15.1.2.15.1	ScatterPlot of Urinary Total NNAL Concentration Adjusted for Creatinine from 24 hour Urine Collection versus 4 hour Urine Fraction at Baseline and Day 90 Visit – FAS
15.1.2.15.2	Bland-Altman Plot for Concordance of Urinary Total NNAL Concentration Adjusted for Creatinine from 24 hour Urine Collection and 4 hour Urine Fraction at Baseline and Day 90 Visit – FAS
15.1.2.16.1	ScatterPlot of Urinary Total 1-OHP Concentration Adjusted for Creatinine from 24 hour Urine Collection versus 4 hour Urine Fraction at Baseline and Day 90 Visit – FAS
15.1.2.16.2	Bland-Altman Plot for Concordance of Urinary Total 1-OHP Concentration Adjusted for Creatinine from 24 hour Urine Collection and 4 hour Urine Fraction at Baseline and Day 90 Visit – FAS
15.1.2.17.1	ScatterPlot of Urinary Total NNN Concentration Adjusted for Creatinine from 24 hour Urine Collection versus 4 hour Urine Fraction at Baseline and Day 90 Visit – FAS
15.1.2.17.2	Bland-Altman Plot for Concordance of Urinary Total NNN Concentration Adjusted for Creatinine from 24 hour Urine Collection and 4 hour Urine Fraction at Baseline and Day 90 Visit – FAS
15.1.2.18.1	ScatterPlot of Urinary 4-ABP Concentration Adjusted for Creatinine from 24 hour Urine Collection versus 4 hour Urine Fraction at Baseline and Day 90 Visit – FAS
15.1.2.18.2	Bland-Altman Plot for Concordance of Urinary 4-ABP Concentration Adjusted for Creatinine from 24 hour Urine Collection and 4 hour Urine Fraction at Baseline and Day 90 Visit – FAS
15.1.2.19.1	ScatterPlot of Urinary 1-NA Concentration Adjusted for Creatinine from 24 hour Urine Collection versus 4 hour Urine Fraction at Baseline and Day 90 Visit – FAS
15.1.2.19.2	Bland-Altman Plot for Concordance of Urinary 1-NA Concentration Adjusted for Creatinine from 24 hour Urine Collection and 4 hour Urine Fraction at Baseline and Day 90 Visit – FAS
15.1.2.20.1	ScatterPlot of Urinary 2-NA Concentration Adjusted for Creatinine from 24 hour Urine Collection versus 4 hour Urine Fraction at Baseline and Day 90 Visit – FAS
15.1.2.20.2	Bland-Altman Plot for Concordance of Urinary 2-NA Concentration Adjusted for Creatinine from 24 hour Urine Collection and 4 hour Urine Fraction at Baseline and Day 90 Visit – FAS
15.1.2.21.1	ScatterPlot of Urinary o-toluidine Concentration Adjusted for Creatinine from 24 hour Urine Collection versus 4 hour Urine Fraction at Baseline and Day 90 Visit – FAS
15.1.2.21.2	Bland-Altman Plot for Concordance of Urinary o-toluidine Concentration Adjusted for Creatinine from 24 hour Urine Collection

TFL number	Title
15.1.2.22.1	and 4 hour Urine Fraction at Baseline and Day 90 Visit – FAS ScatterPlot of Urinary CEMA Concentration Adjusted for Creatinine from 24 hour Urine Collection versus 4 hour Urine Fraction at Baseline and Day 90 Visit – FAS
15.1.2.22.2	Bland-Altman Plot for Concordance of Urinary CEMA Concentration Adjusted for Creatinine from 24 hour Urine Collection and 4 hour Urine Fraction at Baseline and Day 90 Visit – FAS
15.1.2.23.1	ScatterPlot of Urinary HEMA Concentration Adjusted for Creatinine from 24 hour Urine Collection versus 4 hour Urine Fraction at Baseline and Day 90 Visit – FAS
15.1.2.23.2	Bland-Altman Plot for Concordance of Urinary HEMA Concentration Adjusted for Creatinine from 24 hour Urine Collection and 4 hour Urine Fraction at Baseline and Day 90 Visit – FAS
15.1.2.24.1	ScatterPlot of Urinary B[a]P Concentration Adjusted for Creatinine from 24 hour Urine Collection versus 4 hour Urine Fraction at Baseline and Day 90 Visit – FAS
15.1.2.24.2	Bland-Altman Plot for Concordance of Urinary B[a]P Concentration Adjusted for Creatinine from 24 hour Urine Collection and 4 hour Urine Fraction at Baseline and Day 90 Visit – FAS
15.1.2.25.1	ScatterPlot of Urinary HMPMA Concentration Adjusted for Creatinine from 24 hour Urine Collection versus 4 hour Urine Fraction at Baseline and Day 90 Visit – FAS
15.1.2.25.2	Bland-Altman Plot for Concordance of Urinary HMPMA Concentration Adjusted for Creatinine from 24 hour Urine Collection and 4 hour Urine Fraction at Baseline and Day 90 Visit – FAS
15.1.2.26.1	ScatterPlot of Urinary NEQ Concentration Adjusted for Creatinine from 24 hour Urine Collection versus 4 hour Urine Fraction at Baseline and Day 90 Visit – FAS
15.1.2.26.2	Bland-Altman Plot for Concordance of Urinary NEQ Concentration Adjusted for Creatinine from 24 hour Urine Collection and 4 hour Urine Fraction at Baseline and Day 90 Visit – FAS
15.1.2.27.1	ScatterPlot of Urinary 8-epi-PGF 2a Concentration Adjusted for Creatinine from 24 hour Urine Collection versus 4 hour Urine Fraction at Baseline and Day 90 Visit – FAS
15.1.2.27.2	Bland-Altman Plot for Concordance of Urinary 8-epi-PGF 2a Concentration Adjusted for Creatinine from 24 hour Urine Collection and 4 hour Urine Fraction at Baseline and Day 90 Visit – FAS
15.1.2.28.1	ScatterPlot of Urinary 11-DTX-B2 Concentration Adjusted for Creatinine from 24 hour Urine Collection versus 4 hour Urine Fraction at Baseline and Day 90 Visit – FAS
15.1.2.28.2	Bland-Altman Plot for Concordance of Urinary 11-DTX-B2 Concentration Adjusted for Creatinine from 24 hour Urine Collection and 4 hour Urine Fraction at Baseline and Day 90 Visit – FAS

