Smoking will be allowed *ad libitum* from the time of check-in of the subject until around 11:00 PM. Prior to enrolment on Day -2, as the last procedure of the eligibility assessments, subjects will have a product test of the THS 2.2 Menthol (use of up to three THS Menthol Tobacco Sticks). In female subjects, the THS 2.2 Menthol product test will only be done after pregnancy is excluded by a negative urine pregnancy test. Enrolment takes place after all inclusion and exclusion criteria have been satisfactorily met. Only

Data and information contained in this document are considered to constitute trade secrets and confidential commercial information, and the legal protections provided to such trade secrets and confidential information are hereby claimed under the provisions of United States law. No part of this document may be publicly disclosed without the written consent of Philip Morris International.

subjects willing and able to use the product will be enrolled in the study. Subjects who do not meet eligibility criteria on Day -2 will be considered as screening failure until the time of enrolment.

- The baseline period (from Day -1, 06:30 AM until Day 1, 06:29 AM):

All subjects will continue smoking their single preferred brand of mCC *ad libitum*. On Day -1 and Day 0, smoking will be allowed from 06:30 AM onwards until around 11:00 PM. However, on Day 0, smoking will be allowed only after sample for CYP2A6, MNWS and cough questionnaires, and full lung functions have been conducted.

Four-hour urine fraction will be collected on Day-1. On Day 0, 24-hour urine will be collected starting in the morning and ending 24 hours later on Day 1.

On Day 0, subjects will be randomized to 1 of the 3 study arms in a 2:1:1 ratio using a stratified randomization. The full analysis set (FAS) population will be as follows:

- THS 2.2 Menthol Arm: ~80 subjects, *ad libitum* use of the product.
- mCC Arm: ~40 subjects, *ad libitum* use of their preferred mCC brand.
- SA Arm: ~40 subjects who will abstain from smoking.

Subjects will be informed of their randomized study arm by the study site staff on Day 1 prior to 06:30 AM.

- The exposure period (from Day 1, 06:30 AM until time of Discharge on Day 90 Visit (Day 91)):

The exposure period will include both the exposure period in confinement, and the exposure period in ambulatory setting:

- The exposure period in confinement setting (from Day 1, 06:30 AM until time of Discharge on Day 6):

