5. To describe the product use over the course of the study according to the product preference of the subject.

Endpoint:

- Number of mCC or Menthol Tobacco Sticks smoked daily as reported on the usage log during the confinement period and self-reported number of any nicotine/tobacco product use on a daily basis as reported on the product use electronic diary by product preference.

6. To describe the smokers' mental state for the intention to quit smoking at Screening, on Day -2, Day 30 Visit, Day 60 Visit, and Day 90 Visit.

Endpoints:

- By the means of the Prochaska 'stage of change' questionnaire.

7. To describe the changes and reductions in the levels of urinary BoExp and risk markers measured in 4-hour urine fraction on Day 90 Visit in smokers switching from mCC to THS 2.2 Menthol as compared to smokers continuing to smoke mCC and SA.

Endpoints:

- Urinary BoExp (expressed as concentration adjusted for creatinine) in 4-hour urine fraction:
  - MHBMA.
  - 3-HPMA.
  - S-PMA.
  - Total NNAL.
  - 1-OHP.
  - Total NNN.
  - 4-ABP.
  - 1-NA.
  - 2-NA.
  - o-tol.
  - CEMA.
  - HEMA.
  - B[a]P.
  - HMPMA.
  - S-BMA.
- Urinary risk markers (expressed as concentration adjusted for creatinine) in 4-hour urine fraction:
  - 8-epi-PGF2a.
  - 11-DTX-B2.

8. To determine the concordance between the results for BoExp and risk-markers in 24-hour urine and 4-hour urine fraction.

Endpoints:

- MHBMA, 3-HPMA, S-PMA, total NNAL, total 1-OHP, total NNN, 4-ABP, 1-NA, 2-NA, o-tol, CEMA, HEMA, B[a]P, HMPMA, S-BMA, NEQ (expressed as concentration adjusted for creatinine in 24-hour urine collection and concentration adjusted for creatinine in 4-hour urine fraction) at baseline and at Day 90 Visit.
- 8-epi-PGF2a and 11-DTX-B2 (expressed as concentration adjusted for creatinine in 24-hour urine collection and concentration adjusted for creatinine in 4-hour urine fraction) at baseline and at Day 90 Visit.

9. To monitor the BoExp in subjects quitting smoking according to the time since they quit.

Endpoints:

 The reporting of this objective will be the subject of an appendix to the main Clinical Study Report.

 The reporting of this objective will be subject of an appendix to the main Clinical Study Report.

- Carbon monoxide (expressed as ppm) in exhaled breath.
- COHb in blood (expressed as % saturation of hemoglobin)

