**Table 20: Expected Power (YVD-CS01-EU and ZRHX-EX-01 Studies Assumptions)**

Assumptions	Reduction					
	50%	51%	52%	53%	54%	55%
YVD-CS01-EU	94%	88%	81%	70%	56%	38%
ZRHX-EX-01	98%	97%	92%	76%	41%	6%

A total of 160 smokers (80 in THS 2.2 menthol, 40 in mCC, and 40 in the SA arm) will be randomized to demonstrate a reduction of at least 50% on 5 primary BoExp in smokers switching from mCC to THS 2.2 Menthol as compared to those continuing to smoke mCC, using one-sided test with 2.5% type I error probability.

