#### Urinary BoExp Summaries

In general, urinary BoExp will be described over time as follows:

- Summary of concentration values adjusted for creatinine, and their percent change from baseline. Line graphs will be produced for arithmetic means of creatinine adjusted concentration (and 95% CI of the mean) for the percent change from baseline over all timepoints.
- Summary of quantity excreted over 24-hours values.

In general, BoExp measured in blood or breath tests will be described with summaries of the levels over time and levels expressed as percent change from baseline. BoExp levels will also be presented with line graphs.

Summaries and graphs will be produced for the FAS and PP Set. All derived variables will be listed together with the raw BoExp levels.

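### The 4-hour versus 24-hour urine concordance analysis names no statistic that quantifies agreement: read literally, its 95% CI gives only the precision of the mean difference

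*SAP*

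**What the plan says.** The objective in SAP 5.3 is: "To determine the concordance between the results for BoExp and risk-markers in 24-hour urine and 4-hour urine fraction". Protocol 4.2 gives the reason for collecting the 4-hour fraction: "to better understand its accordance with 24-hour urine in the perspective of using such fraction in future ambulatory studies".

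SAP 12.6.3.9 names two displays for each of 18 urinary markers.

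- Scatterplot: "Scatterplots between each pair of variables will be produced showing the Spearman Rank correlation coefficient on the plot".
- Bland-Altman plot: "plots of the data will be produced including the mean of the differences and the 95% CI".

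On population and place of reporting it says: "These will be produced for the FAS and presented in an Appendix of the CSR". The figure titles cover baseline and the Day 90 Visit together and name no arm.

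The section does not mention limits of agreement, the scale of the differences (raw or log), a split by arm, or whether the two time points share one coefficient. Elsewhere the SAP attaches the same interval to a mean, for example in the urinary BoExp summaries of 12.1.3: "and 95% CI of the mean".

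**The concern.** Whether a short collection can stand in for a full one depends on how far the two values differ in the same person. A confidence interval for the mean difference answers another question: how precisely the average bias is known. It narrows as subjects are added, even when individual pairs agree badly.

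A rank correlation answers a third question: whether the two values order subjects alike. It ignores constant bias, and it rises when the sample contains groups at very different exposure levels. Randomization creates such groups by Day 90.

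If the SAP text is programmed as it stands, the appendix will report a narrow interval and possibly a high correlation, and no number for agreement. A reader planning a later ambulatory study could take either one as evidence that the 4-hour fraction is interchangeable with the 24-hour collection.

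**Working it through.** **1. Inputs.** The documents state no sample size, precision or acceptance limit for concordance, so there is no figure to reproduce.

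- n: "A total of 160 smokers (80 in THS 2.2 menthol, 40 in mCC, and 40 in the SA arm) will be randomized" (SAP section 8). Using 160 pairs assumes that every subject has both samples.
- Arm ratios and CVs: SAP Table 16, which holds Day 5 planning values. MHBMA is 0.15 for THS/mCC (CV 0.70) and 1.00 for THS/SA; 3-HPMA is 0.30 (CV 0.50) and 1.70; S-PMA is 0.20 (CV 0.70) and 1.15.
- SA level relative to mCC: 0.15/1.00 = 0.15, 0.30/1.70 = 0.18 and 0.20/1.15 = 0.17.
- Correlation ρ of log 4-hour and log 24-hour values within an arm: not in the documents. Assumed 0 to 0.9.

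The planning inputs were checked against SAP Table 20, with SD = √ln(1+CV²), difference ln(0.5/ratio), one-sided 0.025, and 80:40 subjects (40:40 for Total NNAL). The product of the five powers is 94.3% under the first set of assumptions and 98.2% under the second. Table 20 states 94% and 98%, so the ratios and CVs are read correctly.

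**2. CI of the mean difference against limits of agreement.** With SD the standard deviation of individual differences, the CI half-width is 1.96·SD/√n and the limits are ±1.96·SD. Their ratio is √n. For normal differences, the share inside the CI is 2Φ(1.96/√n) − 1.

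| n | CI half-width | Limits half-width | Ratio | Differences inside CI |
|---|---|---|---|---|
| 40 | 0.310 SD | 1.96 SD | 6.3 | 24% |
| 80 | 0.219 SD | 1.96 SD | 8.9 | 17% |
| 160 | 0.155 SD | 1.96 SD | 12.6 | 12% |

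At n = 160 about 88% of individual differences lie outside the planned interval, whatever the quality of agreement.

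**3. The same contrast as ratios.** For CV 0.70 in both samples, the log SD is √ln(1.49) = 0.63. The SD of the log ratio is 0.63·√(2(1−ρ)). Simulated averages (1,000 runs, n = 160, all at one exposure level):

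| Assumed ρ | CI of mean ratio | 95% limits of agreement |
|---|---|---|
| 0.3 | ×/÷ 1.12 | ×/÷ 4.30 |
| 0.5 | ×/÷ 1.10 | ×/÷ 3.42 |
| 0.7 | ×/÷ 1.08 | ×/÷ 2.60 |
| 0.9 | ×/÷ 1.04 | ×/÷ 1.74 |

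**4. Spearman over all arms.** Simulated lognormal values, 80:40:40, arm levels from step 1:

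| Assumed ρ | MHBMA, Day 90 | 3-HPMA, Day 90 | S-PMA, Day 90 | Baseline, all mCC |
|---|---|---|---|---|
| 0 | 0.53 | 0.61 | 0.49 | 0.00 |
| 0.3 | 0.66 | 0.72 | 0.64 | 0.29 |
| 0.5 | 0.75 | 0.80 | 0.74 | 0.48 |
| 0.7 | 0.85 | 0.87 | 0.84 | 0.68 |
| 0.9 | 0.95 | 0.96 | 0.94 | 0.89 |

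Within the mCC arm the coefficient stays close to ρ (0.47 to 0.48 when ρ = 0.5). At baseline pooling adds nothing, because Protocol 4.1 states: "All subjects will continue smoking their single preferred brand of mCC".

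**5. Constant bias.** Doubling every 4-hour value in the baseline case with ρ = 0.9 leaves Spearman at 0.89.

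**The case against.** The strongest reply is that a Bland-Altman plot is already planned and displays every difference, so wide scatter would be seen. That stands: the spread will be visible, but no planned number describes it.

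The interval may also be loose wording for limits of agreement, and the SAP introduction leaves the detail of the figures to a separate shell document that is not available here. That is possible. The SAP text is still what is specified, and followed as written it puts the wrong lines on the plot.

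A reader might infer more than the documents support.

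- That arms are pooled. This follows only from the FAS label and from titles that name no arm. Neither excludes arm symbols or panels.
- That raw values are used although every other analysis is on the log scale. Section 12.6.3.9 states no scale. SAP section 9 does restrict the comparison to actual values, but the revision history shows that this removed percent change; it does not address transformation. Sections 12.1.3 and 12.6.3.10 also plan arithmetic means. What can be said is that the model-based analyses of these markers (12.6.2.1, 12.6.2.5, 12.6.3.1) use the log scale.
- That the correlation is inflated throughout. It is not at baseline alone. Nor are all markers several-fold apart: Protocol 12.2 works with a 20% difference for 11-DTX-B2. SAP section 8 allows for up to half of the THS arm being excluded from the PP Set in the ambulatory period, mainly for non-compliance. Those subjects stay in the FAS and would narrow the gap between arms.

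SAP 12.6.3.1 also analyses the Day 90 4-hour values with the primary log-scale model. Setting those arm ratios beside the 24-hour ones is informative about group comparisons in later studies. It does not describe agreement within subjects, which is what 12.6.3.9 is for.

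**Conclusion.** The point holds in a limited form. On the literal reading, the planned interval measures the precision of the mean bias and is √n narrower than limits of agreement: 12.6-fold at 160 pairs, less with attrition. Spearman's coefficient is blind to constant bias. If taken over all arms at Day 90, or over both times together, it is raised for markers that differ strongly by arm. The sizes in the working rest on Day 5 planning ratios carried to Day 90, on full separation of the arms, and on assumed within-arm correlations, so they show direction and possible scale rather than a forecast.

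It would go too far to say that the display conceals disagreement, since the individual points are shown. It would also go too far to say that the trial's conclusions are at risk. The objective is exploratory, is reported in a CSR appendix and has no acceptance rule; the protocol speaks of understanding the fraction better, not of validating a replacement. The primary conclusion is unaffected. This is an inexpensive improvement to make.

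**What to change.** In SAP 12.6.3.9:

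- Replace the 95% CI with the 95% limits of agreement and their CIs, computed on the log scale and reported with the mean 4-hour to 24-hour ratio, separately for baseline and Day 90.
- Give Spearman's coefficient by arm as well as overall at Day 90, and never across the two time points.
- State that the baseline pairs come from different days (4-hour sample on Day -1, 24-hour collection from Day 0), so their limits include day-to-day variation as well as the effect of the shorter collection.

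The cost is SAP wording and different lines on figures already planned; no new data are needed. In the same edit, reconcile the figure list with the text: S-BMA is among the 18 markers listed for concordance but has no figure.
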